1.0 TRIAL SUMMARY

Abbreviated Title	Nivolumab Plus Axitinib in Anti-PD1 Refractory Advanced Melanoma
Trial Phase	Phase II
Clinical Indication	Unresectable Stage III or IV Melanoma
Trial Type	Interventional, Clinical Translational
Type of control	Single arm study with historical control
Route of administration	Nivolumab IV, Axitinib PO
Trial Blinding	No
Treatment Groups	1 Arm: Nivolumab plus Axitinib
Number of trial subjects	31
Estimated enrollment period	2.5 years
Estimated duration of trial	4.5 years (2.5 years accrual, up to 2 years on treatment).
Duration of Participation	Up to 2 years
Estimated average length of treatment per patient	Up to 2 years

2.0 TRIAL DESIGN

2.1 Trial Design

This is an investigator-initiated, phase II trial of nivolumab plus axitinib for patients with unresectable stage III or IV melanoma who have progressed on prior anti-PD1 therapy with or without concomitant anti-CTLA4 therapy. Patients will receive treatment with nivolumab 480 mg IV every 4 weeks and axitinib PO 5 mg twice daily. Patients may continue both agents for up to two years if they do not experience progression or dose-limiting toxicity. Biopsies will be taken at baseline and at 12 weeks for an in-depth evaluation of the impact of the combination on the tumor and tumor microenvironment (TME), with an optional biopsy at the time of progression (Figure 1). We have shown that tumor oxidative metabolism and resultant hypoxia are associated with resistance to immunotherapy (IMT). We have shown that in mice, a low dose of axitinib decreases intra-tumoral hypoxia and synergizes with checkpoint inhibitors (ICB) to eradicate melanoma tumors. Thus, we hypothesize that decreasing hypoxia in the TME will re-sensitize melanoma tumors to anti-PD1 immunotherapy and overcome resistance. Blood for research studies will be drawn at baseline (up to 7 days prior to initiation of therapy), at week 12, and at the time of progression. Patients will receive an oral dose of pimonidazole (0.5 g/m²)² before each biopsy to permit in vivo evaluation of intra-tumoral hypoxia. This drug is safe, well-tolerated, and has been previously used in cancer patients to evaluate hypoxia without reported toxicity.³⁻⁵ Pimonidazole hydrochloride (Natural Pharmacia International, Belmont, MA) has IND status for use for the clinical evaluation of hypoxia.³

2.2 Trial Diagram

HCC 20-XXX

Figure 1. Study Schema

OBJECTIVE(S) & HYPOTHESIS(ES)

2.3 Primary Objective(s) & Hypothesis(es)

(1) Objective: To assess the overall response rate (ORR) of nivolumab plus axitinib in patients with anti-PD1 refractory melanoma as measured by clinical tumor measurement and radiologic tumor measurement by CT scans at baseline and after 12 weeks of treatment.

Hypothesis: Patients treated with nivolumab and axitinib will have a response rate greater than the estimated response rate in anti-PD1 refractory patients, which is approximately 10%. We propose this improved response will be due to a reduction of intra-tumoral hypoxia and resultant T cell dysfunction.

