5.1.2.5 Tumor Imaging and Assessment of Disease

PET/CT and CT

- -At baseline and week 12, extra-cranial tumor assessment will be conducted with contrast-enhanced PET/CT or CT and applied using RECIST 1.1 criteria.
- -A screening scan will be performed prior to enrollment unless a recent (within 28 days of enrollment) scan is available. Target and non-target lesions must be identified at time of screening scan and the same lesions must be re-assessed at each restaging scan.
- -Repeat PET/CT or CT imaging will be obtained at week 12, and then CT will be obtained at 12 week intervals.
- -Complete response/partial response confirmation assessments must take place at least 4 and up to 12 weeks after the documentation of initial response. If the last radiographic assessment for extra-cranial disease was more than 8 weeks prior to discontinuation from study and progressive disease has not been documented, disease assessment should be obtained at the time of study discontinuation.
- -If patients have PD by RECIST 1.1 criteria, the Immune Related Response Criteria (irRC) will be used for assessment of tumor response for the purposes of managing patients on protocol treatment and decision making for discontinuation of study therapy due to disease progression. These disease assessments will be performed by the investigator with site radiology reading.
- For the purposes of the secondary efficacy endpoint of the study, response assessment based on RECIST 1.1 will be applied as the primary measure and irRC by investigators will be evaluated as a secondary assessment only if patient have PD by RECIST 1.1. If patients have PD by RECIST 1.1 but have SD or PR by irRC, they will be permitted to continue treatment. In order for a patient to continue to receive study treatment beyond progression by RECIST 1.1, in addition to having SD or PR by irRC, patients must not have symptoms or signs of disease progression, including significantly worse laboratory values or a decline in ECOG performance status.
- At the time of radiographic progression of disease, if treatment is to continue beyond PD, patients will be re-consented and adequately informed of all FDA-approved therapy, and potential clinical benefit, that the patient may be foregoing in order to continue receiving the investigational product.

MRI

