6.3 Sample Size and Accrual

The null hypothesis that the true ORR is 10% will be tested versus a one-sided alternative of 25% or higher, using Simon's minimax two-stage design. In the first stage, 16 patients will be accrued. If there are <2 responses, the study will be stopped and alternative doses of axitinib considered. If at least 2 responses are observed, 15 additional patients will be enrolled in the 2nd stage. The combination therapy will be regarded as worthy of further study if ≥6 responses are observed in both stages. Total sample size is 31 patients. This design has a type I error rate of 0.08 with a power of 0.81 when the true response rate is 0.25. Secondary endpoints of this study are PFS, OS and safety. Survival endpoints (PFS and OS) will be estimated with the Kaplan-Meier method, and compared between marker value groups with the log-rank test. We will also perform extensive correlative analysis (flow, IHC, metabolic analyses).

The accrual rate of the trial is estimated to be 1-2 patients/month, therefore, we will be able to finish the accrual of the study in approximately 24 months.

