6.4.2 Analysis of ORR (Primary)

Overall response rate (ORR) will be estimated by the percentage of patients who achieve CR, PR or SD by RECIST criteria (detailed in Sections 5.1.2.5 and 9.2), with corresponding exact 95% confidence limits being reported. The difference between marker value groups will be examined with Fisher's exact tests.

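### The primary response has no single definition of timing and confirmation, and the plan does not say which definition the 10% and 25% design rates refer to

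*Combined protocol and SAP*

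**What the plan says.** All references are to the combined protocol and SAP.

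- **Section 2.3 (primary objective):** ORR is "as measured by clinical tumor measurement and radiologic tumor measurement by CT scans at baseline and after 12 weeks of treatment". That is two scans.
- **Sections 5.1 and 5.1.2.5 (flow chart, imaging):** the first scan is at week 12 and scans repeat every 12 weeks. "Complete response/partial response confirmation assessments must take place at least 4 and up to 12 weeks after the documentation of initial response". Neither section says how an unconfirmed response enters the ORR.
- **Section 5.1.2.5, on RECIST against irRC:** "For the purposes of the secondary efficacy endpoint of the study, response assessment based on RECIST 1.1 will be applied as the primary measure". ORR is the primary endpoint in Sections 3.2.3.1 and 6.1.
- **Section 6.4.2 (primary analysis):** "Overall response rate (ORR) will be estimated by the percentage of patients who achieve CR, PR or SD by RECIST criteria". There is no time point or confirmation wording of its own, but it refers to Sections 5.1.2.5 and 9.2. Section 9.2 is CTCAE; RECIST is in 9.3.
- **Section 6.4.1:** patients who progress clinically without a scan are given a best response of progressive disease, which suggests a best-response count.
- **Section 6.3 (design):** "The null hypothesis that the true ORR is 10% will be tested versus a one-sided alternative of 25% or higher". "In the first stage, 16 patients will be accrued". "If there are <2 responses, the study will be stopped". "If at least 2 responses are observed, 15 additional patients will be enrolled in the 2nd stage". Success needs at least 6 responses in 31. The stated type I error is 0.08 and the stated power 0.81. The section does not say which response definition the rates or cut-offs use.

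**The concern.** A two-stage rule needs one unambiguous answer per patient to whether that patient responded. Two kinds of patient get different answers here. A patient whose first response is at week 24 is a non-responder under Section 2.3 and a responder under Section 6.4.2. A patient who responds at week 12 and has lost the response at the confirmation scan is a responder under Section 2.3 and a non-responder if confirmation is required.

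The trial is open-label and single-arm, Section 5.1.2.5 has the investigator assess disease with a site radiology reading, and one patient can decide either look. If the definition is left open, it can be settled after the responses are known. The comparison with a historical 10% is also interpretable only if the trial counts responses as that 10% did.

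**Working it through.** **1. Can the sections be read as one definition?**

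A response first seen at week 12 can be confirmed no earlier than week 12 + 4 = 16 and no later than week 12 + 12 = 24 (nominal weeks). Scans at baseline and week 12 therefore cannot establish a confirmed response.

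| Patient | Section 2.3 | Section 6.4.2, own text | If confirmation is required |
|---|---|---|---|
| First response at week 24, later confirmed | no | yes | yes |
| Response at week 12, lost at confirmation | yes | yes | no |
| Stable disease only | no, if response means CR or PR | yes | no |

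**2. Reproducing the stated error rates**

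Inputs from Section 6.3: 16 patients in stage 1, continue with 2 or more responses; 15 more in stage 2, success with 6 or more of 31. With X1 the number of stage-1 responses,

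P(go | p) = Σ over x = 2…16 of P(X1 = x) × P(Bin(15, p) ≥ 6 − x), where X1 ~ Bin(16, p).

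| Stage-1 responses | p = 0.10: probability × needed tail | p = 0.25: probability × needed tail |
|---|---|---|
| 2 | 0.2745 × 0.0556 = 0.0153 | 0.1336 × 0.5387 = 0.0720 |
| 3 | 0.1423 × 0.1841 = 0.0262 | 0.2079 × 0.7639 = 0.1588 |
| 4 | 0.0514 × 0.4510 = 0.0232 | 0.2252 × 0.9198 = 0.2071 |
| 5 | 0.0137 × 0.7941 = 0.0109 | 0.1802 × 0.9866 = 0.1778 |
| 6 or more | 0.0033 × 1 = 0.0033 | 0.1897 × 1 = 0.1897 |
| **P(go), unrounded terms** | **0.0788** | **0.8053** |

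These match the stated 0.08 and 0.81. A search for the minimax design with type I error at most 0.10 and power at least 0.80 returns the same design. The design calculation is correct.

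**3. Sensitivity if the counted rate is not the design rate**

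The documents give no share of late or unconfirmed responses, so every rate below other than 0.10 and 0.25 is an assumption. The formula is the same.

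| Counted rate | Reading | P(go) |
|---|---|---|
| 0.25 | design alternative | 0.805 |
| 0.225 | 10% of responses behind the 25% not counted (0.25 × 0.90) | 0.709 |
| 0.20 | 20% not counted (0.25 × 0.80) | 0.587 |
| 0.28 | looser count than the 25% was set on | 0.888 |
| 0.10 | design null | 0.079 |
| 0.12, 0.13 | looser count than the 10% was set on | 0.152, 0.198 |
| 0.09, 0.08 | stricter count (0.10 × 0.90, 0.10 × 0.80) | 0.052, 0.032 |

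The chance of stopping at stage 1, P(X1 ≤ 1), is 0.063 at 0.25 and 0.141 at 0.20. Power falls below 0.79 once the counted rate is under about 0.2455, that is, once about 2% of responses are lost (0.2455 / 0.25 = 0.98).

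**The case against.** The strongest reply is that nothing in the design calculation is wrong. Section 6.3 states the power for a true response rate of 0.25, and 0.805 holds for whatever definition that rate describes: week 12 or any time, confirmed or not. A reader might infer that the 0.81 fails, or holds under only some readings. The documents do not support that, because no section says the 25% is an any-time or unconfirmed rate. This part of the reply stands.

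Nor do the changes in rate all work against the trial. A stricter count lowers the null rate as well as the alternative, so type I error falls while power falls; a looser count raises both. Claiming an inflated type I error would also require the historical 10% to be a confirmed rate. Section 3.2.3.1 says only that it is based on responses to ipilimumab after anti-PD1 therapy. This stands too, which is why the sensitivity table runs both ways.

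It can also be said that Section 6.4.2 takes in the scan schedule and confirmation text by referring to 5.1.2.5, and that 6.4.1 points to best response. This narrows the gap but does not close it. Section 5.1.2.5 requires confirmation assessments, and a reader might infer that only confirmed responses count, but it never says so. Section 2.3 still names two scans.

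Finally, the reference to a secondary efficacy endpoint in 5.1.2.5 may be meant for PFS, which Section 3.2.3.1 lists as secondary, since the sentence concerns what happens at RECIST progression. Replacing that word with primary could therefore remove a rule that PFS needs.

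**Conclusion.** The point holds as an inconsistency of definition. The sections give different answers for late responses and for responses lost at confirmation, and the 10% and 25% are not tied to any of them. It is not an error in the stated type I error or power, both of which reproduce.

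The size cannot be fixed from the documents. Under the assumed rates, the chance of a positive result moves from 0.805 to between 0.59 and 0.89 at the alternative, and from 0.079 to between 0.03 and 0.20 at the null. What does not depend on those assumptions is that the rule is sensitive to small changes in the count and that one patient can change the decision.

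On timing and confirmation, this should be fixed, preferably before the 16-patient look. Counting SD as response in Section 6.4.2 is a separate defect that could move the rate much further: P(go) would be 0.587 if the null rate of CR, PR or SD were 0.20, and 0.925 if it were 0.30 (assumed rates). Removing SD would leave the timing and confirmation conflict in place.

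**What to change.** 1. State one primary definition in Sections 2.3, 5.1.2.5, 6.3 and 6.4.2. One that fits the existing schedule is best overall response of CR or PR by RECIST 1.1, confirmed at the 4-to-12-week assessment. A week-12 landmark would also be workable if used throughout.
2. Say openly that SD is removed from the definition in 6.4.2, and correct the reference from 9.2 to 9.3.
3. State in 6.3 that the 10% and 25% are on the chosen definition. If the historical 10% was counted differently, say so.
4. Use the definition at both looks, with a fixed stage-1 data cutoff: for example, when all 16 patients have had the week-12 scan and any planned confirmation scan, or have progressed or stopped earlier. Without a cutoff, a best-response count could keep the look open for as long as patients stay on treatment, up to two years.
5. Report the week-12 response rate as supportive.
6. Reword 5.1.2.5 so that RECIST 1.1 is the main measure for the primary ORR as well as for PFS, with irRC secondary for both.

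The cost is a wording amendment, with no added patients or scans. The stage-1 decision waits for confirmation scans that are already scheduled. A first response after the stage-1 cutoff would count at 31 patients but not at the 16-patient look, and the text should say so.

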2.4 Secondary Objective(s) & Hypothesis(es)

(1) Objective: To evaluate the safety of the combination of nivolumab and axitinib.

Hypothesis: The combination of nivolumab and axitinib will be safe and well-tolerated.

(2) Objective: To determine the progression-free survival (PFS) and overall survival (OS) for patients treated with nivolumab plus axitinib.

Hypothesis: Treatment with nivolumab plus axitinib will prolong both PFS and OS.

Exploratory Objectives: Correlative analyses will include and are not limited to evaluation of hypoxia in the TME, TIL function, immune phenotype and tumor cell metabolism.

Hypothesis: Combination treatment will decrease intra-tumoral hypoxia, improve TIL function and yield a more favorable immune infiltrate.

3.0 BACKGROUND & RATIONALE

3.1 **Background**

With the regulatory approval of multiple effective new agents, the treatment paradigm for metastatic melanoma has changed drastically over the past several years. IMT has emerged as a viable and effective treatment for melanoma. However, despite the fact that response rates have increased in patients with advanced disease, only 40% of patients receive benefit from anti-PD1 monotherapy.⁶ While response to the combination therapy (i.e., ipilimumab plus nivolumab) is closer to 60%, it is important to note that over half of these patients experience grade III/IV toxicities.⁷ Furthermore, many patients who initially respond to treatment, later acquire resistance and ultimately progress. The mechanism behind this heterogenous response to IMT remains unclear, and to date, no validated biomarkers can reliably predict response in patients with advanced melanoma. PD-L1 expression, tumor mutational burden, immune gene signatures, and various other predictive biomarkers are under active investigation.^{8,9}

Multiple mechanisms of resistance to IMT may be at play in melanoma. However, one key mechanism is the generation of an immunosuppressive and metabolically harsh TME. ¹⁰⁻¹² The TME is generally considered to be nutrient poor, with decreased essential nutrients for T cell function such as glucose and amino acids, along with concurrent buildup of toxic byproducts such as lactic acid. ¹¹ This altered metabolic landscape is induced by two main drivers: an altered angiogenic pattern as well as the intrinsic deregulated metabolism of the tumor itself. Unrestrained oxidative metabolism in the context of inadequate vasculature results in hypoxia, and increased glycolysis generates an acidic environment. ¹³ T cell effector functions are bioenergetically demanding and require fuel from the local environment. ¹⁰ Thus, despite adequate recruitment, the immune response may be blunted due to T cell dysfunction in part due to a failure to generate the energy required to meet their metabolic needs.

It is important to note that to date, there is no single standard of care to salvage patients who have progressed on IMT. Furthermore, metabolism represents a key, primordial mechanism by which T cells can be regulated, as we propose here.

We have shown that TIL harvested from melanoma-bearing mice have low mitochondrial mass

and depressed glucose uptake. Metabolic profiling of T cells from tumors using Seahorse cell analysis reveals dramatically repressed oxidative function.¹⁴ We have also shown that coinhibitory molecules (PD-1, TIM-3, LAG-3) correlate with both T cell dysfunction and metabolic insufficiency. Thus, as T cells become increasingly 'exhausted', they also display increased metabolic insufficiency.

We have utilized an immunometabolic profiling platform (Figure 2A) that allows comprehensive analysis of the patients' tumor metabolism, immune infiltrate and T cell function, and hypoxia. We have recently shown that tumor cells from a cohort of 30 melanoma patients obtained prior to treatment with **IMT** exist across a wide metabolic spectrum (Figure 2B), with high metabolism oxidative (OCR) and glycolytic metabolism (ECAR),

[figure not shown]

Figure 2. Functionality of melanoma TILs is related to oxidative metabolism of tumor cells. A, Scheme for immunometabolic profiling. B, OCR and ECAR of tumor cells from individual melanoma patients before immunotherapy. C,D, Polyfunctionality (IFN γ and TNF α co-production) in PMA/ionomycin restimulated TILs as a function of tumor cell (C) OCR or (D) ECAR.

hypermetabolic tumors that deregulate both pathways, or more indolent tumors with low metabolic activity. Further, we found that CD8+ TILs isolated from tumors with high OCR (irrespective of tumor cell glycolysis) have significantly decreased polyfunctionality [IFN- γ and TNF- α co-production (**Figure 2C**)], whereas glycolytic capacity of tumors as measured by ECAR did not significantly correlate with T cell functionality (**Figure 2D**).

To evaluate the impact that deregulated oxidative metabolism has on treatment response to anti-PD1, we characterized a cohort of 19 patients with metastatic melanoma just prior to anti-PD1 treatment. Interestingly, patients who did not respond to anti-PD1 checkpoint blockade

[figure not shown]

Figure 3. Tumor cells OXPHOS and consequent hypoxia is correlated with resistance to PD1 blockade in melanoma. A,B OCR (A) and ECAR (B) of tumor cells from patients with progressive disease (NR) or stable disease (partial or complete response, R). C, OR and PFS after anti-PD1 immunotherapy, as a function of tumor cell OCR. D, Carbonic anhydrase IX (CAIX; upregulated by hypoxia) IHC staining in pretreatment biopsies from PD1 non-responders or responders.

(n = 10) had tumor cells characterized by increased oxidative metabolism (**Figure 3A**) while glycolytic metabolism had no strong predictive value (**Figure 3B**). High oxidative tumor cell metabolism was associated with decreased PFS, DOR, and OS (**Figure 3C**) with anti–PD-1 ICB. Of note, anti-PD1 non-responders had increased staining with CAIX, a marker of intratumoral hypoxia. (**Figure 3D**).

Preliminary studies:

We have shown that patients whose tumors have high oxidative metabolism possess high intra-tumoral hypoxia, and that this phenotype is linked with T cell exhaustion dysfunction.1 and Further, oxidative metabolism is associated with decreased PFS, DOR, and OS in patients with advanced melanoma. We have additionally found that tumor cells are more metabolically active after progression on IMT (Figure 4). Thus, strategies to remodel the TME's metabolic landscape are especially important in patients progressing on IMT.

However, as discussed above, patients progressing on anti-PD1 therapy present a new problem their TME has changed to become aggressive, more more immunosuppressive, and even more metabolically deregulated, with altered angiogenic patterns to support this increased metabolic state. As previously described, tumors create a tortuous blood through increased supply expression of VEGF, which creates both zones of hypoxia and highly perfused areas. In cohort of paired 10 melanoma patient samples (at baseline and at progression on anti-PD1), we found that VEGFR1 is variably expressed, VEGFR2 is consistently strongly expressed (consistent with previous studies), VEGFR3 is upregulated in the TME at progression on anti-PD1 (Figure 5). Here, we seek to target the VEGF pathway with axitinib to

[figure not shown]

Figure 4. Tumor cells from melanoma patients who progress on ICB are uniformly hypermetabolic. OCR and ECAR of patient tumor cells pre-treatment (subdivided by response, as previously published) or obtained at

[figure not shown]

Figure 5: VEGFR expression in tumor biopsies from patients prior to anti-PD1 and at progression. Paired

[figure not shown]
[figure not shown]

Figure 6. Low-dose axitinib reduces intratumoral hypoxia. Hypoxia staining by anti-pimo antibodies of B16 melanoma. Tumor-bearing mice received vehicle or axitinib at high or low dose for 4 days. Mice were pulsed with pimo before being euthanized. While high-dose axitinib exacerbates hypoxia, low-dose axitinib lowers intertumoral hypoxia.

correct the vasculature and restore metabolic balance to promote a better immune response. Axitinib is a VEGF receptor small molecule tyrosine kinase inhibitor with demonstrated safety and tolerability when combined with anti-PD1. ^{15,16} Further, axitinib has high inhibitory activity for VEGFR1, 2, and 3, which are each involved in altered angiogenesis. We hypothesize that by modulating/correcting angiogenesis, axitinib will decrease intra-tumoral hypoxia and thus reduce T cell dysfunction. We have shown that a low dose of axitinib is superior to a higher dose of axitinib in reducing intra-tumoral hypoxia in B16 melanoma (Figure 6). This finding is significant because we previously demonstrated that intra-tumoral hypoxia is associated with T cell exhaustion and decreased T cell effector function. ¹ We have also performed pre-clinical experiments with anti-PD1 plus axitinib in murine models. Here, axitinib was given concurrently in B16 melanoma (generally insensitive to ICB) or in MC38 adenocarcinoma (partially sensitive to anti-PD1). The combination of low dose axitinib and ICB (CTLA4+PD1 in B16, PD1 monotherapy in MC38) provided an improved and durable response in both models (Figure 7).

We hypothesize that decreasing hypoxia in the TME will re-sensitize melanoma tumors to anti-PD1 therapy. We have chosen to use axitinib because it has already been safely combined with anti-PD1 therapy and was overall well-tolerated ^{15,16}. Importantly, the standard dose of axitinib (5 mg BID) corresponds to the low dose used in our murine models. The combination of pembrolizumab plus axitinib was superior to sunitinib in patients with advanced renal cell carcinoma, leading to FDA approval for combination treatment. ¹⁵ In addition, while axitinib has been combined with anti-PD1 in mucosal melanoma patients with promising results, this study was done in the front-line setting and did not include the extensive correlative analyses we propose. ¹⁶ Taken together, based on previously published work and data from our laboratories, we hypothesize that axitinib can metabolically remodel the TME to render it

more sensitive to ICB, specifically by reducing intra-tumoral hypoxia, increasing T cell infiltration, and increasing polyfunctional T cells.

